3.6.2. Adverse Event Definitions

3.6.2.1. Adverse Events

Information about all local and systemic AEs, whether volunteered by the subject, discovered by Investigator questioning, or detected through other means, will be collected and recorded on the AE CRF and followed as appropriate.

An AE is defined as any untoward medical occurrence in a patient or clinical investigation subject administered a pharmaceutical product (or cosmetic product), which does not necessarily have a causal relationship with this treatment. An AE can therefore, be any unfavorable and unintended sign, symptom, or disease temporally associated with the use of a medicinal investigational product, whether or not considered related to the medicinal investigational product.

Adverse Events will be coded using an internationally recognized medical dictionary for regulatory activities (MedDRA).

Medical conditions/diseases present before starting study treatment are considered AEs only if they worsen after starting study treatment (any procedures specified in the protocol). Any AEs occurring before starting study treatment but after signing the ICF are recorded on the Medical History/Current Medical Conditions CRF.

To the extent possible, each AE will also be described by:

- 1. its duration (start and end dates),
- 2. the severity grade (mild, moderate, severe),
- 3. its relationship to the study drug,

- 4. the action(s) taken, and
- 5. as relevant, the outcome.

Note: Any observed response which can be denoted using the irritation criteria summarized in Table 3 and Table 4 will not be considered an AE. Likewise, any tape-related irritation will not be noted as an AE.

3.6.2.2. Serious Adverse Events

A "SAE" is any AE that:

- Results in death;
- Is life-threatening (Note: the term "life-threatening" refers to any AE that, as it occurs, puts the subject at immediate risk of death. It does not refer to an AE that hypothetically might have caused death if it were more severe).
- Results in hospitalization or prolongation of current hospitalization (not including hospitalization for a pre-existing condition that has not increased in severity or frequency from the subject's underlying medical condition prior to entry into the study).
- Is a congenital anomaly/birth defect in the offspring of a subject.
- Is another serious (important medical events) event.
- Results in persistent or significant disability/incapacity.

(Note: Important medical events may not be immediately life-threatening or result in death or hospitalization but may be considered serious when, based on the appropriate medical judgment, they may jeopardize the subject or require medical or surgical intervention to prevent one of the outcomes listed above. Examples of such medical events include allergic bronchospasm requiring intensive treatment in an emergency room or at home; blood dyscrasias or convulsions that do not result in inpatient hospitalization; or development of drug dependency or drug abuse.)

3.6.2.3. Severity of Adverse Events

"Severity" of the AE refers to the extent to which an AE affects the subject's daily activities and differs from "Serious," which is a regulatory classification.

The Investigator is to classify the severity of an AE according to the following definitions:

- **Mild:** The symptom has a negligible effect or no impairing effect on the subject's normal function.
- Moderate: The symptom impairs the subject's normal function to some extent.
- Severe: The symptom has an obvious, significantly impairing effect on the subject's normal function.

3.6.2.4. Relationship of Adverse Events to Study Treatments

The Investigator is to classify the drug relationship of an AE according to the definitions outlined in Table 5.

Association	Definition
Not related	 (1) the existence of a clear alternative explanation (e.g., mechanical bleeding at surgical site) or (2) non-plausibility, e.g., the subject is struck by an automobile or cancer developing a few days after drug administration.
Unlikely	There is no medical evidence to suggest that the AE may be related to study drug usage, or there is another more probable medical explanation.
Possible	There is medical evidence to suggest that there is a reasonable possibility that the AE may be related to study drug usage. However, other medical explanations cannot be excluded as a possible cause.
Probable	There is strong medical evidence to suggest that the AE is related to study drug usage.
Definite	A clinical event, including laboratory test abnormality (if applicable), in which there is no uncertainty in its relationship to test drug (e.g., positive Rechallenge).

Table 5:Relationship of AE to Study Drug

3.6.3. Reporting Adverse Events

Adverse events that occur from first dose through completion of the last study visit should be reported. All SAEs, regardless of causality, occurring from the time of informed consent until 30 days following study completion OR until 30 days after the subject's last application of study medication, whichever is longer, must be reported to TKL Clinical Safety within 24 hours of the knowledge of the occurrence (this refers to any adverse event that meets any of the aforementioned serious criteria). SAEs occurring after the 30-day follow-up period AND considered related to study drug must also be reported to the Sponsor.

Every attempt should be made to describe the AE in terms of a diagnosis. If a clear diagnosis has been made, individual signs and symptoms will not be recorded unless they represent atypical or extreme manifestations of the diagnosis, in which case they should be reported as separate events. If a clear diagnosis cannot be established, each sign and symptom must be recorded individually.

Any SAEs occurring in a subject receiving study drug must be reported to the Sponsor within 24 hours of the site being informed of the event, even if the event does not appear to be drug-related. The report must be made by sending a completed SAE Report form to the Sponsor. Any pertinent follow-up information should be provided in a similar manner. Contact information is provided in Section 3.7.1.

3.6.4. Adverse Event Follow-up

Any ongoing AE at the time of study completion or withdrawal will be followed until the AE is resolved or the subject is referred to his/her own PMD. The Investigator and the Sponsor will

decide if longer follow-up is appropriate on a case-by-case basis. Subjects who experience any clinically significant AE will remain under medical supervision until the Investigator or the Sponsor's Medical Monitor deems the AE to be resolved, stabilized, or no longer serious enough to warrant follow-up.

3.6.5. Pregnancy reporting

Prior to study enrollment, females of childbearing potential must be advised of the importance of avoiding pregnancy during study participation and the potential risk factors for an unintentional pregnancy. The signed Informed Consent Form must document this discussion.

A UPT will be performed on all females of childbearing potential at Day 1 (day of first patch application) and EOS. All women of childbearing potential will receive a UPT prior to the first study drug administration and the study drug must be withheld until the results of laboratory pregnancy testing are available. If pregnancy is confirmed, the subject must not receive any study drug and must not be enrolled in the study.

3.6.6. Expected Adverse Events

Any observed response in the patch test area that can be denoted using the irritation criteria summarized in Table 3 and Table 4 will not be considered an AE.

Tape related reactions will only be recorded as AEs when the subject is discontinued due to tape reaction around all sites. When 1 or 2 sites are experiencing severe tape related reactions, the application site will be stopped and the subject will continue on the study.

3.7. Instructions for Rapid Notification of Serious Adverse Events

3.7.1. Contact person and number

Serious adverse events must be reported immediately (i.e., not later than 24 hours after first knowledge) by e-mail with the scanned TKL SAE report form to:

3.7.2. **Reporting Responsibility**

Any death, SAE, pregnancy, (see Section 3.6), or unusual frequency of AEs, must be reported immediately (i.e., not later than 24 hours after first learning of its occurrence) to the Sponsor's study manager by the Investigator, even if the event(s) appear to be unrelated to study treatment. Follow-up information about a previously reported SAE or pregnancy must also be reported to the Sponsor within 24 hours of receiving it. If the SAE has not been previously documented (i.e., is a new occurrence) and it is thought to be related to the IP (or therapy), the Sponsor may contact the Investigator to obtain further information. If warranted, an investigator alert may be

issued to inform all Investigators involved in any study with the same product (or therapy) that this SAE has been reported.

The IRB should also be notified of SAEs or pregnancies and of any follow-up information in writing, as is practical, and depending on local regulations.

3.7.3. Reporting procedures

For each SAE, the Investigator will complete a SAE Report Form in English and assess the relationship of each SAE to study treatment. The completed form(s) should be sent by e-mail to the Sponsor within 24 hours of first knowledge of the SAE (as outlined in Section 3.7.1 and Section 3.7.2). The initial SAE should be reported immediately, even if only preliminary information is available. Follow-up information should be sent by the same Investigator, restating the date of the original report. Either a new SAE form is sent (stating that it is a follow-up), or the original one is resent (with the new information highlighted and a new date provided). The follow-up should describe whether the event has resolved or continues, if and how it was treated, whether the blind was broken or not, and whether the patient continued or discontinued study participation. The form confirmation will be retained.

Pregnancy follow-up (as outlined in Section 3.6.5) should be reported to the IRB within 24 hours of first knowledge on a Pregnancy Report Form. Follow up will describe the outcome of the pregnancy, including any voluntary or spontaneous termination, details of the birth, and the presence or absence of any congenital abnormalities or birth defects.

3.8. Appropriateness of Safety Measurements

The safety assessments in the study are standard safety measures in clinical trials.

4. STATISTICAL METHODS

4.1. General Considerations for Data Analysis

The focus of the statistical analysis will be the comparison with controls of the phototoxic response to the study products. The parameter for phototoxicity will be the mean of Day 3 and 4 scores (sum of erythema and edema).

All statistical processing will be performed using the SAS[®] system (version 9.2 or higher). No interim or subgroup analyses are planned.

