[name]

Clinical Study Protocol CCP-020 (Diacerein 1%) Topical Ointment Sponsor Protocol No. CCP-020-104 TKL Study No. PB610317

A 4 Day, Randomized Study to Evaluate the Potential of CCP-020 (Diacerein 1%) Topical Ointment to Induce a Phototoxicity Skin Reaction in Healthy Subjects, Using a Controlled Photopatch Test

Author: Document type: Development Phase: Document Date: Document Status Number of Pages:

Clinical Study Protocol 1 23-October-2017 Amendment 1 **38**

Property of **Castle Creek Pharmaceuticals, LLC**. Confidential May not be used, divulged, published, or otherwise disclosed without the consent of **Castle Creek Pharmaceuticals, LLC**.

Synopsis

Study Title:	A 4 Day, Randomized Study to Evaluate the Potential of CCP-020 (Diacerein 1%) Topical Ointment to Induce a Phototoxicity Skin Reaction in Healthy Subjects, Using a Controlled Photopatch Test
TKL Study Number:	PB610317
Sponsor Protocol Number:	CCP-020-104
Sponsor:	Castle Creek Pharmaceuticals, LLC
Development Phase:	1
Study Objectives:	To determine the potential of CCP-020 (Diacerein 1%) Topical Ointment and vehicle ointment to cause irritation when topical application to skin is followed by light exposure.
Study Design:	On Day 1, CCP-020 (Diacerein 1%) Topical Ointment and vehicle ointment will each be applied to 2 sites on the lower thoracic area of the back under fully occlusive patches for approximately 24 (\pm 2) hours. This will be the only application during the study. Minimal erythema dose (MED) irradiation will also be performed for each subject on Day 1. After patch removal on Day 2, all application sites will be evaluated and one application site of each study product will be irradiated with 16 J/cm ² of Ultraviolet A (UVA) followed by 0.5 times the MED of UVA/Ultraviolet B (UVB) irradiation. An additional site will also be irradiated with 16 J/cm ² of UVA followed by 0.5 times the MED of UVA/UVB and will serve as an untreated control. On Day 3, approximately 24 hours (\pm 4 hours) after irradiation and Day 4, approximately 48 hours (\pm 4 hours) after irradiation, all application sites and the untreated control site will be evaluated.
Planned Sample Size:	30 evaluable subjects
Study Population:	Healthy adult male and female volunteer subjects

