3. INVESTIGATIONAL PLAN

3.1. Study Design

This is a single-center, randomized, within-subject comparison study of CCP-020 (Diacerein 1%) Topical Ointment and vehicle ointment. CCP-020 (Diacerein 1%) Topical Ointment and vehicle ointment will each be applied to 2 sites, one which will be irradiated and one which will remain non-irradiated. The irradiated and non-irradiated sites will be compared with each other and with an untreated irradiated control.

A total of 4 application sites (2 cm x 2 cm each) will be marked on the subject's lower thoracic area of the back: 2 sites on each side of the back – 2 sites for CCP-020 (Diacerein 1%) Topical Ointment and 2 sites for vehicle ointment. Each study product will be applied according to the randomization scheme in an amount of 0.2 mL under occlusive patch conditions once during the study.

Approximately 24 (\pm 2) hours post study product application, the patches will be removed by study staff. The sites will then be graded for cutaneous reactions by a trained evaluator and the designated sites, including the untreated site, will be exposed to irradiation. One side of the back will be designated for irradiation and the other side will remain non-irradiated. An additional site will be marked on the "irradiated side" of the back which will receive no treatment, but will receive irradiation to serve as an untreated irradiated control. The sites and control will be examined at approximately 24 and 48 hours post irradiation and graded for reactions. Cutaneous reactions at the application sites will be evaluated using a visual scale that rates the degree of erythema, edema, and other signs of cutaneous irritation (see Table 3 and Table 4).

Safety evaluations include collection of adverse events (AEs).

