3.4.5.2. Blinding

Investigative personnel who are involved in the preparation/application and removal of the treatments (CCP-020 [Diacerein 1%] topical ointment and vehicle ointment) will be unblinded and will not perform the evaluation of skin responses. The trained evaluator who will be evaluating skin responses will be blinded to IPs and the treatment allocation; however, because of the demarcations/skin coloration remaining on the skin following patch removal, complete blinding of the evaluators cannot be completely assured.

Investigative personnel, including the Investigator and the trained evaluator involved in the evaluation of responses, will remain blinded during the course of the study until Database Lock and finalization of the Statistical Analysis Plan (SAP).

In the event of an emergency, if possible, the Investigator or designee will contact the Sponsor with notification of the intent to unblind the treatment codes prior to the actual unblinding. If it is not possible to notify the Sponsor prior to the unblinding, the Investigator or designee will contact the Sponsor immediately following the unblinding procedure and follow with a written notification to document the exact manner in which the code was broken and the justification for the unblinding. The Investigator will communicate the treatment identification to only the investigative personnel who require the information to manage the emergency. Unblinding will happen on site at TKL.

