On Day 4, approximately 48 (\pm 4) hours after irradiation (ie, approximately 72 (\pm 4) hours following product application), all application sites and the untreated control site will be evaluated. Adverse events and concomitant medications will be reviewed and recorded, as appropriate. A UPT will be performed for female subjects of childbearing potential.

Retest

Although not all observations of erythema and edema are associated with phototoxicity, erythema and edema must be observed for a reaction to be suspected of being a positive phototoxic reaction. An increase in the intensity of the reaction over time further supports an assessment of phototoxicity. If a reaction is observed at both the irradiated and non-irradiated product sites (ie, if contact sensitization or irritation may have occurred), the reaction upon retest must be at least one grade more intense at the irradiated site than at the non-irradiated site for the reaction to be suspected of being a phototoxicity reaction (refer to Section 3.5.7 for response grades and notations).

If it is determined by the Investigator that a retest should be performed, then the retest patches will be applied as soon as the original reactions have resolved. The Investigator will determine the patch conditions to use during the Retest (see Section 3.4.3). The study material will be applied to naive sites on the back, using appropriate patches to further discriminate a phototoxic reaction from an irritation reaction. Identical patches will be applied to sites previously unexposed to the study material. Approximately 24 (\pm 2) hours later one site will be irradiated with 16 J/cm² of UVA followed by ½ MED of UVB radiation using a filtered light source. An additional untreated site will be irradiated with 16 J/cm² of UVA followed by ½ MED of UVB radiation using a filtered light source. An

be evaluated upon patch removal and approximately 24, 48, and 72 hours after irradiation. Concomitant medications and AEs will also be reviewed.

In some cases the retest may be done on the individual ingredients of the products.

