3.5.7. Safety Assessments

3.5.7.1. Patch Test Site Evaluations

Assessment of the application sites will be done once daily, Days 1-4. Assessment of the untreated irradiated control site will be done once daily on Days 2, 3 and 4.

The symbols listed in Table 3 and their respective numerical equivalents will be used to express the response observed at the time of examination. Additional response notations are presented in Table 4.

Table 3:Response Scores

Response	Symbol	Numerical Equivalent Score
Erythema		
No reaction	-	0
Mild, but definite erythema	+	1
Moderate erythema	++	2
Marked/severe erythema	+++	3
Edema		
No reaction	-	0
Mild, but definite edema	**	1
Definite edema with erosion/vesiculation	***	2

Table 4:Notations

Response/Comment	Notation
Hyperpigmentation	Hr
Hypopigmentation	Но
Vesiculation	V
Papular response	р
Papulovesicular response	pv
Damage to epidermis: oozing, crusting, and/or superficial erosions	D
Itching	Ι
Spreading of reaction beyond patch study site (ie, reaction where material did not contact skin)	S
Follicular irritation with or without pustule formation (folliculitis)	f
Subject absent	Х
Patch dislodged	PD
Not patched	NP
No reaction	0

Before results are interpreted as indicative of phototoxicity, the subject(s) must first be retested to the product(s) to demonstrate that the results obtained are reproducible.

If the non-irradiated study product sites give reactions indicative of significant primary irritancy or prior sensitization, it may not be possible to make any comments about phototoxic potential. In such situations, further routine patch evaluation might be recommended.

Because of the relatively small number of subjects evaluated in this study, it will generally not be possible (except in extreme cases) to categorize a product as having mild, moderate or severe phototoxic potential.

The readings will be made under a standardized white light source. The numerical equivalent scores will be used for calculations.

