4.6. Safety Evaluation

4.6.1. Local Tolerability Assessment

All assigned scores during the study for subjects who complete the study will be summarized using frequency counts by treatment for Days 2, 3 and 4. Selected pairwise comparisons will be performed on the mean of the Day 3 and Day 4 response scores (sum of erythema and edema

scores) in the context of the analyses of variance (ANOVA). Pairs to be compared are: each study product irradiated versus non-irradiated and all pairwise comparisons on each side (CCP-020 [Diacerein 1%] topical ointment versus vehicle ointment on both the irradiated and non-irradiated sides and CCP-020 [Diacerein 1%] topical ointment versus untreated and vehicle ointment versus untreated on the irradiated side).

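### Should the pre-irradiation Day 2 grade be a covariate in the comparison of irradiated with non-irradiated sites of the same product?

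*Combined protocol and SAP*

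**What the plan says.** The synopsis sets the order of events on Day 2: "After patch removal on Day 2, all application sites will be evaluated and one application site of each study product will be irradiated". Section 3.1 agrees, with light coming after the grading: "The sites will then be graded for cutaneous reactions by a trained evaluator and the designated sites, including the untreated site, will be exposed". The Day 2 grade of a product site therefore cannot reflect light.

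Section 4.1 defines the outcome without it: "The parameter for phototoxicity will be the mean of Day 3 and 4 scores (sum of erythema and edema"). Section 4.6.1 compares that mean pairwise within an ANOVA. The pairs include each product's irradiated against its non-irradiated site. No covariate is named. Scores from all three days "will be summarized using frequency counts by treatment for Days 2, 3 and 4", which is the only stated use of Day 2.

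Three other provisions matter. Under Retest in Section 3.5.1, "An increase in the intensity of the reaction over time further supports an assessment of phototoxicity", and where both product sites react, "the reaction upon retest must be at least one grade more intense at the irradiated site than at the non-irradiated site". Section 3.5.7.1 requires a reproducible retest before any result is read as phototoxic. It adds that, if non-irradiated sites show significant irritancy or prior sensitization, "it may not be possible to make any comments about phototoxic potential". Section 3.4.5.2 says that the investigator and the evaluator "will remain blinded during the course of the study until Database Lock and finalization of the Statistical Analysis Plan (SAP"), so a separate SAP was still to be completed.

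**The concern.** A trial statistician who sees a pre-exposure measurement on the same sites and scale as the outcome expects it in the model. Here it qualifies as a baseline: for two sites of the same product, light is the only planned difference, and it comes after the Day 2 grade. If occlusion or the ointment irritates one site more than the other and this lasts to Days 3 and 4, it adds noise to the one contrast that isolates light. With 30 subjects and no power calculation, avoidable noise could hide a real phototoxic signal. The plan also treats a rise over time as supporting evidence case by case, but leaves it out of the ANOVA.

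A side issue strengthens the impression. The Day 2 text in Section 3.5.1 can be read as having the staff who remove the patches also grade the sites, whereas Section 3.4.5.2 bars removal staff from grading.

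**Working it through.** **The plan's own figure.** Section 4.2 gives 30 evaluable subjects by convention, with no alpha, effect size, SD or power, so it cannot be reproduced. Two-sided alpha of 0.05 is assumed below. With n = 30 a paired t-test has 80% power at a difference of 0.53 SD of the paired difference.

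**What the planned contrast already removes.** Write a site's Day 3/4 score as subject effect + site-specific irritation + light effect (irradiated site only) + error. In irradiated minus non-irradiated, the subject effect drops out. What remains besides light is the difference in site-specific irritation, plus error. Day 2 can help only with the part of that difference that is already visible on Day 2 and persists.

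**Gain as a function of correlation.** Let r be the correlation between the Day 2 and Day 3/4 paired differences. Adjustment multiplies the variance by (1 - r²) × (1 + 1/(n - 3)) = (1 - r²) × 28/27.

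- Break-even: r² = 1/28, so r is about 0.19.
- r = 0: factor 1.037, equivalent n = 30/1.037 = 28.9, power 78.5% instead of 80%.
- r = 0.3: factor 0.944, equivalent n 31.8, power 82.1%.
- r = 0.5: factor 0.778, equivalent n 38.6, power 88.7%.

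The documents do not give r, so even the sign of the change is unknown.

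**Can the slope be estimated?** Suppose a share p of sites is irritated on Day 2, and a subject's two sites share one draw with probability s. The two sites then differ with probability q = (1 - s) × 2p(1 - p). All 30 differences are zero with probability (1 - q)^30.

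| p | q (s = 0.5) | all zero, s = 0.5 | all zero, s = 0.9 | at least 5 of 30 differ, s = 0.5 |
|---|---|---|---|---|
| 5% | 0.0475 | 23% | 75% | 1% |
| 10% | 0.09 | 6% | 58% | 13% |
| 20% | 0.16 | 0.5% | 38% | 54% |

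The last column is the binomial upper tail. A covariate therefore needs a fallback rule. A rule that adjusts only when at least 5 differences are non-zero is almost never triggered when irritation is rare.

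**Simulated change in power.** The 0/1 model assumes n = 30, s = 0.5, light adding 1 point in 20% of subjects, no late irritation, and 20,000 trials per setting. Entries are percentage points relative to the unadjusted paired test, at persistence 0.2 / 0.5 / 0.8.

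| p | no rule | 5-difference rule |
|---|---|---|
| 5% | 0.0 / 4.7 / 11.3 | 0.0 / 0.2 / 0.3 |
| 10% | 0.5 / 6.1 / 16.1 | 0.2 / 1.4 / 3.1 |
| 20% | 1.6 / 7.6 / 18.8 | 1.4 / 5.1 / 12.0 |

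The large gains come from adjusting without a rule, in a model where every reaction without light is already visible on Day 2. An ordinal model that allows late reactions was run over 108 settings:

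- No rule: -7.3 to +16.0, median -0.8; 31 settings lose more than 2 points.
- 5-difference rule: -2.3 to +15.9, median -0.1; 16 settings gain more than 2, 2 lose more than 2, and the other 108 - 16 - 2 = 90 lie within 2 points. With 5% of sites reactive, the range is -0.4 to +1.9.

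**Against the planned analysis.** The rule's gains and losses above are measured against a stand-alone paired t-test. The plan calls for pairwise comparisons within an ANOVA. Under an assumed subject-block ANOVA with pooled error over all five sites, the ANOVA had higher power than the rule in all 18 settings tried. That is not clean evidence for the ANOVA, because its rejection rate under no effect reached 7.7%. It does leave the rule's benefit over the planned analysis unproven.

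**The case for a change.** The best case for adjusting is that the grades are already collected, the SAP is not final, and fixing a rule now would prevent a choice made after seeing unbalanced Day 2 reactions. If a fifth of sites react, the reactions differ between a subject's two sites and they persist, the gain is real: about 12 points with the rule and about 19 without. Type I error stayed near 5%. Section 3.4.5.1 also does not clearly state that the irradiated side is itself randomized, which gives some value to checking that the sites were alike before light.

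Part of this stands. A covariate for this one contrast would be legitimate, and the SAP may add one. Nothing in the documents suggests that the favourable setting applies, though. Section 1.1 reports good tolerability; this is not occlusive-patch evidence, so it is only suggestive, but it points towards rare reactions, where the rule does almost nothing. If non-irradiated sites are markedly irritated, Section 3.5.7.1 already warns that phototoxic potential may not be assessable. The Day 2 frequency counts also put the reactions before light on record.

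On who grades, the Day 2 sentence in Section 3.5.1 is loosely worded. It can be read as referring to the clinical staff collectively. Section 3.1 gives grading to a trained evaluator, and Section 3.4.5.2 says that those who apply or remove patches do not grade. The Day 2 grade is in any case outside the planned inference.

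**Conclusion.** The concern does not hold. It identifies a real feature of the plan: the Day 2 grade precedes light and is used only descriptively. That is not an error. The within-subject contrast is valid without it, irritation shared by a subject's sites cancels, and no bias follows if the two sites are comparable before irradiation. The only thing at stake is precision. With a workable safeguard the median change in power is about zero (-0.1 points over 108 settings), with a worst loss of 2.3 and a best gain of 15.9; without the safeguard losses reach 7.3. These figures assume two-sided 0.05 and invented irritation rates, persistence and tracking, because the documents supply none. They also take a paired t-test as comparator, not the planned ANOVA.

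Power for this contrast does not by itself settle the study's conclusion, since a reproducible retest must precede any reading of phototoxicity. Whether to add the covariate is a matter of preference that a statistician could settle either way in the SAP. Only the supplied text could be checked, and the separate SAP may already address the point.

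### The only tested phototoxicity readout is a mean score that one reactor in 30 cannot make significant, and no subject-level reactor count with an interval is planned

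*Combined protocol and SAP*

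**What the plan says.** Section 4.1 sets the analysis variable: "The parameter for phototoxicity will be the mean of Day 3 and 4 scores (sum of erythema and edema"). Section 4.6.1 says how it is tested: "Selected pairwise comparisons will be performed on the mean of the Day 3 and Day 4 response scores", within an ANOVA. The contrasts are "each study product irradiated versus non-irradiated and all pairwise comparisons on each side", which makes six. The model terms, the error term, the significance level and any multiplicity rule are not given. The same section adds a descriptive output, in which all assigned scores of completers are "summarized using frequency counts by treatment for Days 2, 3 and 4".

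The subject-level rules are elsewhere. Under Retest in Section 3.5.1, "erythema and edema must be observed for a reaction to be suspected of being a positive phototoxic reaction". If both the irradiated and the non-irradiated product sites reacted, the retest reaction must be "at least one grade more intense at the irradiated site than at the non-irradiated site". Section 3.5.7.1 requires a reproducible result on retest before anything is read as phototoxicity. Table 3 there scores erythema 0 to 3 and edema 0 to 2 (the top edema grade is "Definite edema with erosion/vesiculation"), so a site can total at most 5.

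Section 4 contains no variable, count, rate, confidence interval or retest summary built on these subject-level rules.

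**The concern.** The protocol recognises a phototoxic reaction subject by subject, but the analysis tests a group average. Phototoxicity may appear in only a few subjects, and an average over 30 dilutes a few strong reactions. The summed score also discards the distinction Section 3.5.1 relies on: 2+0 and 1+1 both total 2, but only the second shows both signs.

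The other planned outputs do not fill the gap. Frequency counts by treatment show that a high score occurred, but not whether the same subject's non-irradiated site also reacted. Sections 3.6.1, 3.6.2.1 and 3.6.6 exclude any response gradable with Tables 3 and 4 from the adverse events, so a strong site reaction does not reach those tables either. At stake is whether the report can say how many subjects reacted, how many were confirmed, and what reaction rate 30 subjects can exclude.

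**Working it through.** **Inputs from the documents.** N = 30 evaluable subjects (Section 4.2). Five conditions per subject: two products, each irradiated and non-irradiated, plus one untreated irradiated site (Section 3.1). Score range 0 to 5 (Table 3). The sample size rests on convention, with no power, effect size or SD, so there is no plan figure to reproduce.

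**Assumptions.** Two-sided 0.05 per contrast, with 0.05/6 = 0.0083 as a sensitivity. In the base case, k subjects have the same Day 3/4 mean s at the irradiated CCP-020 site, and every other score is 0.

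**Formula.** In a subject + site ANOVA on m sites:
- difference in means = ks/30
- residual SS = s²·k(1 − k/30)·(m − 1)/m on 29(m − 1) df
- MSE = s²·k(1 − k/30)/(29m)
- t² = (ks/30)² / (2·MSE/30) = (29m/60)·k/(1 − k/30)

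The score s cancels, so severity does not affect the p-value. Here m = 2 is the paired t-test (29 df), m = 3 the irradiated side only (58 df) and m = 5 all sites (116 df). The irradiated-side model serves only the contrasts on that side.

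| Reactors k | Paired: t, p | Irradiated side: t, p | Five sites: t, p |
|---|---|---|---|
| 1 | 1.00, 0.326 | 1.22, 0.226 | 1.58, 0.117 |
| 2 | 1.44, 0.161 | 1.76, 0.083 | 2.28, 0.025 |
| 3 | 1.80, 0.083 | 2.20, 0.032 | 2.84, 0.005 |
| 4 | 2.11, 0.043 | 2.59, 0.012 | 3.34, 0.001 |

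For example, k = 1 and m = 5 gives t² = (145/60)·1/(29/30) = 2.5. A one-way ANOVA on five sites has the same t² on 145 df and practically the same p. At 0.0083, among k = 1 to 3, only three reactors in the five-site model pass. A reactor scoring the maximum on both days moves the mean by 5/30 = 0.17.

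**With background erythema.** The documents give no background rate. Simulation (1,000 replicates per setting) used grade 1 erythema at 10% to 50% of sites and reactors scoring 3 to 5. The chance of p < 0.05 in the five-site model was about 7–14% for k = 1, 17–65% for k = 2 and 32–99% for k = 3. With a paired error term it was at most about 20% for k = 1 to 3. With no reactors, rejection rates were about 4–6%, so one reactor adds little.

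**What a subject-level rate would give.** Exact (Clopper-Pearson) 95% intervals at n = 30:
- 0/30: 0 to 11.6%, from 1 − 0.025^(1/30)
- 1/30: 0.1 to 17.2%
- 2/30: 0.8 to 22.1%
- 3/30: 2.1 to 26.5%

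The chance of seeing at least one reactor, 1 − (1 − p)^30, is 60%, 79% and 96% for true rates of 3%, 5% and 10%.

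**Would testing the rate be more sensitive?** No. Exact McNemar for k against 0 gives p = 2·(1/2)^k, which is 0.0625 at k = 5 and 0.031 at k = 6. It needs six reactors.

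**The case against.** A reader might infer that the mean cannot respond to one, two or three reactors. The documents do not support that. They name an ANOVA, not a paired t-test, and if error is pooled over the five sites, two and three reactors reach p = 0.025 and 0.005 in the base case. Only the single-reactor statement holds under every model tried.

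A reader might also infer that a non-significant ANOVA will be reported as no phototoxic potential. No section says so. Section 3.2 refers interpretation to working criteria, Section 3.5.7.1 demands reproduction on retest, and the frequency counts would show a severe score. An individual reactor would probably be noticed.

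Nor does the protocol hold a ready-made responder definition. Section 3.5.1 makes erythema and edema necessary, not sufficient, and its one-grade rule applies on retest when both product sites reacted. Making a criterion built from these pieces the lead readout would be a preference, not a correction. Section 3.4.5.2 also mentions an SAP to be finalised, so the gap can be asserted only of the text available here.

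These points limit the claim but do not remove it. The route by which reactors would be noticed depends on the Investigator's decision to retest, and Section 4 commits to no count, rate or interval from it.

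**Conclusion.** The point holds in a limited form. The mean Day 3/4 sum is the only tested readout, and it cannot separate 2+0 from 1+1. With other scores at 0, one reactor in 30 cannot make it significant at two-sided 0.05, whatever the severity. Whether two or three do depends on the unspecified error term. The level of 0.05, the zero scores elsewhere and the simulated background rates are assumptions; the p-values illustrate sensitivity and do not predict the result.

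The firmer half needs no such assumption: the protocol has subject-level rules and a retest, and its analysis section reports neither. This is an inexpensive improvement that should be made. It does not invalidate the planned ANOVA.

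**What to change.** In Sections 4.1 and 4.6.1, keep the ANOVA and report 95% confidence intervals for its contrasts. Add one subject-level table, specified in advance, for CCP-020 and for vehicle:

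- (a) n/N with exact 95% interval for subjects with both erythema and edema at the irradiated site on Day 3 or Day 4, cross-tabulated against the same subject's non-irradiated site for that product;
- (b) n/N with exact 95% interval for subjects retested, and for those confirmed on retest under the rule already in Section 3.5.1.

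If the one-grade excess is also applied to the Day 3/4 readings, label it as an adaptation of the retest rule.

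The cost is a few lines of text and one table from data the protocol already collects. The count is coarse, its upper limit at 0/30 is 11.6%, and testing the rate would be less sensitive than testing the mean, so it should be presented as an estimate with an interval beside the ANOVA.
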